#### **14.2.1.1. Perimetric Mean Deviation Power**

We summarise here the estimated power for detecting differences between arms in the PMD outcome measure. In the NORDIC trial [Wall, 2014], the authors observed that the improvement from baseline to 6-months in PMD was 0.71dB greater in the experimental arm than the control arm. Cross-sectional SD of PMD was 1.1-1.2 at baseline. Table 2 in their publication shows that the standard error of mean PMD is higher at 6m than at baseline, likely reflecting a combined effect of missing data at 6-months and greater variability of post-baseline measures. We plan to take repeated measures of PMD at baseline, 2 weeks, 1-month (m), 2m, 3 m, 4m, 5m and 6m. Assuming that the overall SD of PMD scores is 1.8, thus introducing some reasonable inflation on Wall *et al.*'s baseline variability parameter for the reasons identified, using the formula given on p.31 of Diggle, Liang & Zeger (1994) we would expect to require 142 patients in total to detect a difference of 0.71dB (justified below) with 90% power at a 5% significance level, if the serial correlation between repeated measures is 0.4 (and we expect a value in this region) [Diggle, 1994]. If the serial correlation parameter is as low as 0.3, the required sample size increases to 166.

Study Number: INVEX-CLIN-IIH-301 Protocol	Compound No.: Presendin
	Version: 5.0 for EU countries dated 08Dec2022

Note that the method used above assumes full follow-up and data collection. Although every effort will be made to collect all outcomes, naturally some missing data is expected. If we inflate the maximum sample size identified above by up to 30% to account for some data loss, we require up to  $166 / 0.7 = 237$  patients. The assumed 30% missing data rate was adjudged to be realistic by the Sponsor based on previous trials in IIH. Thus, we expect to be able to cover the impact of missing data using the extra patients necessitated by the sample size calculation for ICP.

The above assumes only one eye is measured per patient. In actuality, some patients may provide outcomes for both eyes because any eye that satisfies the eligibility criteria (see Section 5.2) will be enlisted in the study. Put another way, all patients will provide outcomes in at least one eye, and some will provide outcomes in two. Second eyes will naturally be highly correlated with first eyes. From a sample size perspective, this means the additional information in second eyes will be of modest value. Nevertheless, outcomes on second eyes will contain some additional information and should be included in the analysis in the interest of efficiency. When estimating sample size, for the sake of simplicity and because of uncertainty in the rate of eligibility in second eyes, we have assumed that each patient yields outcomes from only one eye. Eligible second eyes will be included in the analysis with appropriate model terms to handle the within-patient correlation (further details are included in the SAP). As such we expect outcomes from second eyes to provide a modest uplift in power to the scenarios presented here.

This section assumes a longitudinal analysis method such as hierarchical regression.

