### 14.1. Hypotheses

This trial compares outcomes in IIH patients under Presendin and matched placebo. The primary hypothesis that will be tested is:

- The ICP measurement in the Presendin group is equal to the ICP measurement in the placebo group at Week 24; against the alternative that the outcomes differ

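### The PMD sample sizes of 142 and 166 do not follow at a two-sided 5% level from the eight visits listed; for a two-sided slope comparison, 240 patients with 30% loss give about 84–89% power, not 90%

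*Protocol*

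**What the plan says.** Section 14.2.1 names ICP and PMD as the outcomes the trial was sized for. Section 14.2.1.1 (Perimetric Mean Deviation Power) gives these inputs for PMD:

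- Effect: in the earlier acetazolamide trial the "improvement from baseline to 6-months in PMD was 0.71dB greater in the experimental arm than the control arm".
- Variability: "Assuming that the overall SD of PMD scores is 1.8".
- Visits: "We plan to take repeated measures of PMD at baseline, 2 weeks, 1-month (m), 2m, 3 m, 4m, 5m and 6m".
- Error rates: "with 90% power at a 5% significance level", with no statement of one or two sides.

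The result is that the trial would "require 142 patients in total to detect a difference of 0.71dB (justified below) with 90% power at a 5% significance level" at a serial correlation of 0.4, and "If the serial correlation parameter is as low as 0.3, the required sample size increases to 166". The formula is given only as a page reference to a textbook. The section then computes 166 / 0.7 = 237 and concludes: "Thus, we expect to be able to cover the impact of missing data using the extra patients" that the ICP calculation brings. The following text assumes one eye per patient and a longitudinal analysis. Section 14.1 states the primary (ICP) hypothesis as equality "against the alternative that the outcomes differ", which is two-sided. No hypothesis is written for PMD.

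**The concern.** A reader who puts the listed inputs into a standard repeated-measures formula at a two-sided 5% level does not get 142 or 166, but figures about 23% larger. PMD is one of the two sizing outcomes, and 166 is the number behind 237 and so behind the statement that 240 patients absorb 30% loss. If 166 is too small for the test intended, that statement fails, and the protocol promises more power for its leading secondary endpoint than the trial has.

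**Working it through.** **Which formula.** The protocol's N rises as the correlation falls, and 142/166 = 0.855, close to (1 − 0.4)/(1 − 0.3) = 0.857. That is how a comparison of slopes behaves. A time-averaged comparison moves the other way: two-sided on eight visits it needs 130 at 0.4 and 106 at 0.3. So a slope formula is inferred:

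n per arm = 2(z_α + z_β)² · SD² · (1 − ρ) / (Sxx · δ²)

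**Inputs (all from section 14.2.1.1).** SD = 1.8; δ = 0.71/6 = 0.1183 dB per month; 90% power, so z_β = 1.2816; ρ = 0.4 or 0.3. The visit times in months are 0, 0.5, 1, 2, 3, 4, 5, 6. Their sum is 21.5 and their sum of squares 91.25, so Sxx = 91.25 − 21.5²/8 = 33.47. Hence Sxx · δ² = 33.47 × 0.01400 = 0.4687.

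**Reproducing the printed figures.**

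- One-sided 5%, eight visits: (1.6449 + 1.2816)² = 8.564. At ρ = 0.4, n = 2 × 8.564 × 3.24 × 0.6 / 0.4687 = 71.05 per arm, total 142.1. At ρ = 0.3 the total is 165.8. These are 142 and 166 to the nearest whole number.
- Two-sided 5%, with the week -1 screening field added at −0.25 months and δ kept at 0.71/6: Sxx = 41.14, totals 141.8 and 165.5. Rounded up, these are also 142 and 166. If the 0.71 dB is instead spread over 6.25 months, the match is lost (154 and 180).

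**Two-sided 5% on the eight listed visits.** (1.9600 + 1.2816)² = 10.507.

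| ρ | n per arm | total, unrounded | total, even for 1:1 | after 30% loss |
|---|---|---|---|---|
| 0.4 | 87.17 | 174.3 | 176 | 176/0.7 = 251.4, so 252 |
| 0.3 | 101.70 | 203.4 | 204 | 204/0.7 = 291.4, so 292 |

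**Power at the planned size.** 240 × 0.7 = 168 evaluable, 84 per arm. The standard error of the slope difference is 1.8 × √((1 − ρ)/33.47) × √(2/84).

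- ρ = 0.4: SE = 0.0372; 0.1183/0.0372 = 3.18; 3.18 − 1.96 = 1.22; power 88.9%.
- ρ = 0.3: SE = 0.0402; 0.1183/0.0402 = 2.95; 2.95 − 1.96 = 0.99; power 83.8%.

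At the printed sizes with complete data, two-sided power is 83.3% (142 at ρ = 0.4) and 83.4% (166 at ρ = 0.3).

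**The case against.** Several points on the other side have weight.

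- **A one-sided test is not proven.** A reader might infer that the sponsor used a one-sided test. The match is close, but the nine-measure two-sided calculation matches as well, and a screening perimetry is scheduled at week -1 in Table 1. On that reading 168 evaluable patients give about 94% (ρ = 0.4) or 90% (ρ = 0.3), and the coverage claim is true. Against it, the power section lists eight measures starting at baseline, so the text would still misstate its inputs.
- **Formula and sidedness are inferred.** The cited page is not reproduced, and section 14.1 covers ICP only. The ICP powers do not settle the matter. They reproduce two-sided (85.4% and 91.0%) only if a baseline correlation of 0.4 is assumed, which the protocol does not give. One-sided with no correlation comes close too (86.8% and 91.6%). Two-sided remains the natural reading, since nothing in the protocol declares a one-sided test.
- **The contrast matters.** Section 14.3.1.5 defines the PMD estimand as a difference over 24 weeks. If that means a time-averaged difference, 168 patients give more than 95% two-sided power. A reader might go the other way and judge power by a single week-24 comparison. The protocol assumes a longitudinal analysis and does not show that contrast to be the planned one, so no weight is put on it.
- **The inputs are cautious.** The SD of 1.8 is raised from 1.1–1.2 at baseline, the loss is modelled as patients who contribute nothing, and second eyes are ignored. With complete data, 240 patients give 96.7% or 94.1% two-sided.

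These points limit what can be concluded. None of them makes 142, 166 and 237 follow two-sided from the visits as listed.

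**Conclusion.** The stated PMD sample sizes do not reproduce at a two-sided 5% level from the inputs printed beside them. If the test is a two-sided slope comparison on the eight visits, the requirement after 30% loss is about 252 (ρ = 0.4) or 292 (ρ = 0.3), against 240 planned, and power is about 89% or 84%. At the correlation the protocol expects, the shortfall is about one percentage point. The material gap, about six points, is at ρ = 0.3, the case from which 237 was derived. The conclusion rests on the inferred slope formula, a two-sided reading for PMD, one eye per patient, and 30% of patients contributing no data.

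A reader might go further and conclude that the trial is too small for PMD. The documents do not support that: an unlisted ninth measure or a time-averaged contrast would bring power to 90% or above. What is established is that the printed figures and the coverage claim cannot both stand on the listed inputs with a two-sided slope test.

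**What to change.** In section 14.2.1.1 (Perimetric Mean Deviation Power), state the sidedness, the visits and the contrast (slope or time-averaged) behind the figures. Then:

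- **Two-sided slope comparison on the eight listed visits:** replace 142, 166 and 237 with 176, 204 and 292 (252 at ρ = 0.4), state about 84–89% power for 240 randomised with 30% loss, and remove the claim that the loss is covered.
- **Screening field used as a ninth measure:** correct the visit list instead, and say over what interval the 0.71 dB is taken. The sample sizes and the coverage claim can then stand if the slope is kept at 0.71/6 per month.
- **One-sided test or time-averaged contrast meant:** say so. For a time-averaged contrast the figures need recalculating, because 142 and 166 do not come from that formula.

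The cost is protocol wording only. In the first case the stated PMD power becomes less favourable. No extra patients are proposed.

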#### **14.2.2. Stratification**

At the outset, it is expected that markers of disease severity will be prognostic of potential efficacy. For this reason, it is proposed to stratify randomisation by, baseline ICP ( $<35\text{cm}$  or  $\geq 35\text{ cm}$ ), baseline body mass index ( $< 30\text{ kg/m}^2$  or  $\geq 30\text{ kg/m}^2$ ) and baseline PMD (worse than or equal to  $-3.5\text{dB}$  or better than  $-3.5\text{dB}$ ).

#### **14.2.3. Sample Size Sensitivity**

##### **14.2.3.1. Clinically Meaningful Effect Sizes**

Minimally relevant effect sizes have not been fully determined in IIH given it is a rare disease with relatively few previous trials.

The ICP diagnostic threshold in IIH is 25 cm CSF [Mollan, 2018]. However, it is not necessary to reduce ICP  $<25\text{ cm CSF}$  to achieve remission from signs and symptoms of IIH in all patients [Sinclair, 2010]. The clinical importance of a particular change in ICP will vary depending on the starting ICP and the impact this pressure has on vision and

Study Number: INVEX-CLIN-IIH-301 Protocol	Compound No.: Presendin
	Version: 5.0 for EU countries dated 08Dec2022

headache. Changes in ICP of 5 cm CSF are generally considered meaningful when treating IIH patients. For example, in a clinical study evaluating the benefits of weight loss in IIH patients, a 16.5% (6.2 cm CSF) reduction in ICP resulted in a statistically significant improvement in headache and vision measures as well as quality of life [Sinclair, 2010]. In the IIH Treatment trial (n=165), a study evaluating the drug treatment acetazolamide against placebo, a reduction of -5.9 cm CSF was seen in association with significant improvement in PMD, OCT measures of papilloedema and quality of life measures [Wall, 2014].

The minimally clinically important change in the perimetric mean deviation adopted into clinical practice was established by the Neuro-Ophthalmology Research Disease Investigator Consortium (NORDIC) group and the IIH Treatment Trial (IIHTT). The investigators found a 0.71dB difference in the PMD between the two trial arms (comparing acetazolamide with placebo) that was clinically meaningful. The change of 0.71dB was interpreted as clinically meaningful as this was accompanied by significant changes in LP opening pressure, papilloedema (measured by OCT), general quality of life and visual related quality of life [Wall, 2014, Bruce, 2016].

The clinically meaningful effect size for MHD reflects that for a phenotypically similar headache, chronic migraine. Recent randomised trials in patients with chronic migraine [Tepper, 2017; Silberstein, 2017], episodic migraine [Goadsby, 2017], or both [Camporeale, 2018] have shown in post-baseline months 1–3, odds of migraine relative to baseline of 0.5–0.8 with placebo and 0.5–0.3 with experimental drugs. Decreases in MHD relative to baseline grew in time, and placebo responses were stronger in chronic migraine than episodic migraine. In the three placebo-controlled, blinded trials, these equated to odds-ratios of migraine compared with placebo of 0.8–0.6, or absolute differences of 1.5–2.5 MHD [Sinclair, 2010; Tepper 2017; Silberstein, 2017; Goadsby, 2017].

#### **14.2.4. Trial Stopping Criteria**

There are no trial-specific stopping rules.

The following events, if applicable, may cause premature termination of the clinical study or study arms:

- unjustifiable risk and/or toxicity in risk-benefit analysis (decision taken by sponsor or representative), e.g. when adverse events occur, unknown to date in respect of their nature, severity, duration or frequency in relation to the current established safety profile (substantial changes in risk-benefit considerations), and therefore medical and/or ethical reasons affect the continued performance of the study;

Study Number: INVEX-CLIN-IIH-301 Protocol	Compound No.: Presendin
	Version: 5.0 for EU countries dated 08Dec2022

- new scientific evidence becomes available during the study that could affect the patient's safety (benefit-risk analysis no longer positive), e.g. new insights from other clinical trials;
- request of the sponsor with or without recommendation from the data safety monitoring committee, or of a regulatory agency, e.g. as a consequence of inspection;
- favourable opinion withdrawn by the ethics commission;
- in case of difficulties in the recruitment of the planned number of subjects in the indicated time (insufficient recruitment rate); -withdrawal of the license to manufacture and/or of the permission to import, it must either be adjusted or the clinical study/trial must be discontinued.

### **14.3. Data Analysis Considerations**

#### **14.3.1. Estimands**

We have specified intercurrent events that are material to the measurement of our primary and secondary outcomes, and unbiased estimation of treatment effects attributable to Presendin.

ICP-lowering medication include: acetazolamide, topiramate, diuretics, glucocorticoids (oral dexamethasone and oral prednisolone). Headache-preventative medications include: amitriptyline, topiramate, nortriptyline, beta blockers, candesartan, sodium valproate, pizotifen, botox, CGRP-therapy.

##### **14.3.1.1. Outcome: Intracranial pressure (ICP)**

###### **14.3.1.1.1. Intercurrent event: ICP-lowering medications**

All patients are expected to have elevated ICP because it is a defining characteristic of the disease. ICP is a physiological variable that is unlikely to show spontaneous improvement without treatment. For these reasons, we expect ICP-lowering medication use to be greater in the placebo arm. If a patient takes medication that is intended to reduce their ICP, it is logical to expect that their ICP will be reduced. Outcomes from patients that take ICP-lowering medications will confound the estimation of the causal treatment effect of Presendin. We have no data to estimate the length of effects of ICP-lowering medications. For these reasons, we propose to remove 24-week ICP outcomes from all patients that have used ICP-lowering medications and replace these observations with arm-specific imputations. This will allow estimation of the treatment effect that is

Study Number: INVEX-CLIN-IIH-301 Protocol	Compound No.: Presendin
	Version: 5.0 for EU countries dated 08Dec2022

purely and causally attributable to Presendin. Patients will consent at enrolment to forgo the use of ICP-lowering medications and be informed that taking ICP-lowering medications during the trial would constitute rescue therapy and a treatment failure and be a protocol deviation.

#### **14.3.1.1.2. Intercurrent event: Off-protocol lumbar punctures**

Lumbar punctures are commonly conducted to reduce intracranial pressure [Weisberg, 1977; Johnston, 1981; De Simone, 2005]. In some centres, they are given routinely although this has now been advised against in the International IHH Guidelines (Soler, 1998; Mollan, 2018). As such, they remain a material therapeutic option. LP is expected to reduce ICP mean opening pressure 32 (28-37) cm CSF to 19 (17-21) cm CSF post LP [Yiangou, 2019]. Beneficial effects dissipate with time and whilst there has been no longitudinal assessment to quantify change in ICP after an LP, it is expected that effects in the majority of change would have dissipated completely within two months [Yiangou, 2019]. Outcomes from patients that have undergone off-protocol LPs will confound the estimation of the causal treatment effect of Presendin. For these reasons, we propose to remove 24-week ICP outcomes from all patients that have had an off-protocol LP within two months of the protocol-scheduled 24-week LP and replace these observations with arm-specific imputations. Where patients require off-protocol LP this would be a protocol deviation.

#### **14.3.1.1.3. Inter-current event: Dramatic weight-loss**

Research has shown that weight loss in IHH is associated with reductions in IHH symptoms, including decreases in ICP [Sinclair, 2010]., Sudden dramatic weight loss, e.g. arising from a surgical procedure will likely yield material changes to IHH symptoms. This will confound the estimation of the causal treatment effect of Presendin. For these reasons, we propose to remove 24-week ICP outcomes from all patients that experience weight loss exceeding 10% of baseline weight after a surgical weight-loss procedure and replace with arm-specific imputations. Patients will be ineligible for the trial if they have had a surgical weight-loss procedure within 3 months of randomisation or fail to confirm that they do not intend to undertake such a procedure during the trial. They will also be informed at enrolment that undergoing a surgical weight-loss procedure would be a protocol deviation.

#### **14.3.1.2. Outcome: Perimetric Mean Deviation (PMD)**

##### **14.3.1.2.1. Intercurrent event: ICP-lowering medications**

All patients are expected to suffer from some visual field loss at enrolment because it is the hallmark feature of the disease [Wall, 2014; Ottridge, 2017; Markey, 2020]. If a

Study Number: INVEX-CLIN-IIH-301 Protocol	Compound No.: Presendin
	Version: 5.0 for EU countries dated 08Dec2022

patient takes ICP-lowering medication (rescue medication due to treatment failure), it is logical to expect that their ICP will decrease and that papilloedema will reduce as a result, allowing visual fields to improve. As stated, we expect ICP-lowering medication use to be greater in the placebo arm. Outcomes from patients that take these medications will confound the estimation of the causal treatment effect of Presendin. For these reasons, we propose to remove the PMD outcomes following the administration of ICP-lowering medications and replace these observations with imputations generated by a method suitable for longitudinal data imputation. Outcomes recorded at the unscheduled visit when the treatment failure is confirmed (and just prior to starting ICP lowering medication) will be defined as the last analysed visit. This will allow estimation of the treatment effect that is purely and causally attributable to Presendin.

#### **14.3.1.2.2. Intercurrent event: Off-protocol lumbar punctures**

As discussed above, LPs are a material and widespread intervention in the treatment of IIH, given with the intention of reducing intracranial pressure and improving the associated symptoms of the disease, including reducing pressure on the optic nerve and papilloedema, allowing visual fields to improve. Patients that have LPs are expected to experience less pressure on the optic nerve, less papilloedema, and have better chances of their visual fields improving. Beneficial effects dissipate with time and whilst there has been no longitudinal assessment to quantify papilloedema after an LP the consensus of clinicians would predict that effects of the LP on papilloedema and therefore visual fields would have dissipated by one month. Outcomes from patients that have undergone off-protocol LPs will confound the estimation of the causal treatment effect of Presendin. PMD outcomes will be recorded repeatedly during the trial. For the reasons stated, we propose to remove PMD outcomes recorded in the 4-weeks following an off-protocol LP, and replace these observations with patient-within-arm imputations generated by a method suitable for longitudinal data imputation.

#### **14.3.1.2.3. Intercurrent event: Dramatic weight-loss**

Research has shown that weight loss in IIH is associated with reductions in IIH symptoms, including improvements in visual fields [Sinclair, 2010]. Sudden dramatic weight loss, e.g. arising from a surgical procedure will likely yield material changes to IIH symptoms. This will confound the estimation of the causal treatment effect of Presendin. For these reasons, we propose to remove PMD outcomes of patients that experience weight loss exceeding 10% of baseline weight after a surgical weight-loss procedure from the date of procedure. These outcomes will be replaced with patient-within-arm imputations generated by a method suitable for longitudinal data imputation.

Study Number: INVEX-CLIN-IIH-301 Protocol	Compound No.: Presendin
	Version: 5.0 for EU countries dated 08Dec2022

**14.3.1.3. Outcome: Papilloedema measured by OCT (optic nerve head size, retinal nerve fibre layer)**

**14.3.1.3.1. Intercurrent event: ICP-lowering medications**

All patients will suffer from papilloedema at enrolment as it is the hallmark feature of the disease [Wall, 2014; Ottridge, 2017; Markey, 2020]. If a patient takes ICP-lowering medication, it is logical to expect that their ICP will decrease and that the papilloedema will reduce in turn. As stated, we expect ICP-lowering medication use to be greater in the placebo arm. Outcomes from patients that take these medications will confound the estimation of the causal treatment effect of Presendin. For these reasons, we propose to remove the OCT outcomes following the administration of ICP-lowering medications and replace these observations with imputations generated by a method suitable for longitudinal data imputation. Outcomes recorded at the unscheduled visit when the treatment failure is confirmed (and just prior to starting ICP lowering medication) will be defined as the last analysed visit. This will allow estimation of the treatment effect that is purely and causally attributable to Presendin.

